6.7 Multicenter Study

This study is expected to enroll 3150 participants at up to 50 sites in US. Data from all sites are pooled, but site is a covariate in the immunogenicity ANOVA models described in Section 6.1.

Except for lot consistency analyses, PXVX0317 lots are pooled as the PXVX0317 treatment group.

6.8 Subgroup Analysis

Summaries pool all age groups and are repeated separately for each age group. Analyses of the primary immunogenicity and safety endpoints are also summarized by sex, race, and ethnicity group along with treatment group. AEs are reported by product lot subgroup.

6.9 Multiplicity Adjustment

6.9.1 Coprimary Immunogenicity Endpoints

The familywise error rate is fixed at a two-sided alpha of 0.05 by the requirement that all coprimary endpoints must be met for a successful outcome: seroresponse at a titer of (H_{A1}) , GMT (H_{A2}), and lot consistency pairwise GMT ratios (H_{A3}). See Section 6.4 for formal statistical hypotheses. Note that success on the Day 22 lot consistency endpoint is only required for FDA.

For each individual coprimary endpoint, the primary time point is Day 22 and the primary analysis population is the IEP. For the seroresponse and GMT endpoints, the primary analysis is for the pooled age strata; no multiplicity adjustment is made for the analysis of the mITT population or of the separate age strata as the primary population is the combined age groups in the IEP. For the lot consistency pairwise GMT ratios, the primary analysis is for the 18 to <46 years of age stratum; again, no multiplicity adjustment is made for the analysis of the mITT population as the primary population is the IEP.

6.9.2 Key Secondary Immunogenicity Endpoints

Seroresponse key secondary immunogenicity endpoints are tested using a prespecified hierarchical strategy to preserve the type I error rate without the need for further multiplicity adjustment. These endpoints are tested formally only if the null hypotheses are rejected for all coprimary endpoints and only until a nonsignificant test is reached. If a nonsignificant test is reached formal testing stops, and the remaining endpoints are reported for information only. The sequential order of the seroresponse rate difference key secondary endpoints (H_{A4}) is Days 15, 183, and 8, each for the IEP across all age groups combined. At Day 15, the endpoint is tested for the success criterion of the lower bound of the two-sided Newcombe hybrid score method 95% CI on the difference in seroresponse rates between PXVX0317 and

placebo and superiority to placebo using a two-sided chi-square test with alpha=0.05. At Day 183 and Day 8, only superiority to placebo using a two-sided chi-square test with alpha=0.05 is tested.

- 1. Day 15 seroresponse at a titer of including superiority to placebo and the success criterion of the lower bound of the two-sided Newcombe hybrid score method 95% CI on the difference in seroresponse rates between PXVX0317 and placebo
- 2. Day 183 seroresponse at a titer of **series** including superiority to placebo.
- 3. Day 8 seroresponse at a titer of **series** including superiority to placebo.

After testing the coprimary immunogenicity endpoints and, if all met, the hierarchical key secondary immunogenicity endpoints, no other formal hypothesis testing is performed. The remaining secondary immunogenicity endpoints involving GMTs, GMFI, other titers, the exploratory endpoint, and all safety endpoints are evaluated and reported for information only, thus no further multiplicity adjustment is needed.

7 STUDY POPULATION CHARACTERISTICS

7.1 Participant Disposition

Participant disposition over the course of the study is summarized for all randomized participants by treatment group, including number and percentages of participants still in the study each scheduled visit, competing the study and reason for not completing the study. Screen failure reasons are listed by participant. The number and percentage of participants enrolled by site are provided by treatment group for all randomized participants.

Randomization details including site, stratum, date and time of randomization, kit number, randomized treatment group assignment, and actual treatment received including lot number are listed by participant. Participants randomized but not treated, those receiving the wrong treatment, or receiving an incorrect dose are listed. Participants who were randomized despite not meeting entry criteria and those who received an excluded concomitant medication are listed.

7.2 **Protocol Deviations**

Protocol deviations defined in Section 5.1 are categorized as important or not important and evaluated for exclusion of participants from analysis populations. Important protocol deviations are tabulated by category and by treatment group for the randomized population as well as listed by participant.

8 IMMUNOGENICITY ANALYSIS

8.1 **Populations Analyzed**

The number and percentage of participants in each analysis population (randomized, exposed, safety, mITT, IEP) are summarized by treatment group for all participants. Reasons

for exclusion from analysis populations are summarized by treatment group for all randomized participants and listed by participant.

8.2 Demographics and Baseline Characteristics

8.2.1 Demographics

Demographic and baseline characteristics including age, age stratum, sex, race, ethnicity, baseline height, weight and body mass index, and baseline anti-CHIKV SNA serostatus (positive or negative) are tabulated by treatment group for the randomized, safety, mITT, and IEP populations for all ages pooled and by age strata. Participant site assignment is evident from the unique participant identifier.

8.2.2 Baseline Disease Characteristics

This study enrolls healthy US adolescent and adult participants 12 to <65 years of age, so no baseline disease characteristics are collected.

8.2.3 Medical History

Medical history is coded to the MedDRA dictionary SOC and PT (see Section 5.8). A summary table and a listing of medical history are supplied by treatment group for the randomized population.

8.2.4 Prior and Concomitant Medications and Vaccines

Prior medications are defined as those taken within 30 days prior to the screening visit (90 days for blood products) through the start of IP administration on Day 1 (baseline). Concomitant medications are defined as those taken after start of IP administration on Day 1 (baseline) through the end of study. See definitions in Section 6.3. Partial dates are imputed according to Section 6.5.2.

Prior and concomitant medications and vaccines are coded to the WHODrug Global Dictionary ATC classification and preferred drug name (see Section 5.8). All prior and concomitant medications and vaccines are tabulated together by ATC classification, preferred drug name, and treatment group for the safety population; a second similar table contains only concomitant vaccines. A participant data listing of all prior and concomitant medications is generated.

8.3 Treatment Compliance

As the IP administration is a single 0.8 mL intramuscular injection performed by site personnel, measurements of treatment compliance are not applicable. A vaccine administration summary is provided and details listed.

8.4 Immunogenicity Analysis

Summary statistics for immunogenicity results by scheduled visit for each treatment group are provided for the IEP and mITT populations, unless otherwise specified. Anti-CHIKV SNA seroresponse rates and GMTs are tabulated by visit for each treatment group. Geometric mean fold increase as well as number and percentage of participants meeting anti-CHIKV SNA titers of ≥ 15 and 4-fold rise from baseline are also displayed by postvaccination scheduled visit for each treatment group. Reverse cumulative distribution plots of anti-CHIKV SNA titer versus percentage of participants in each treatment group are generated by scheduled visit for the IEP. Anti-CHIKV SNA GMT are also plotted over time for each treatment group for the IEP.

The primary analysis of all immunogenicity endpoints utilize the IEP across all age groups combined. As specified for individual endpoints below, primary and secondary immunogenicity analyses of anti-CHIKV SNA seroresponse rates and GMTs are repeated using the mITT population as a measure of robustness of results. All immunogenicity analysis are repeated in the separate age strata for the IEP, and primary and secondary immunogenicity analyses of anti-CHIKV SNA seroresponse rates and GMTs are repeated in the separate age strata for the mITT population as well. No multiplicity adjustment is made for the analysis of the mITT population or of the separate age strata as the primary population is the combined age groups in the IEP. In addition, the primary immunogenicity endpoints using the IEP across all age groups combined are repeated by sex, by race group (white and non-white), and by ethnicity group (Hispanic or Latino and Not Hispanic or Latino).

8.4.1 Coprimary Immunogenicity Endpoints

8.4.1.1 Day 22 Treatment Group Estimates and Difference in Anti-CHIKV SNA Seroresponse Rates

The superiority of PXVX0317 vaccine immunogenicity over that of placebo is illustrated at Day 22 by estimating the treatment-specific seroresponse rates and by calculating the difference in seroresponse rates between the two treatment groups (the percentage of participants with an anti-CHIKV SNA titer PXVX0317 minus placebo) and associated 95% CI. See Section 6.1 for statistical details.

This endpoint is summarized for all age strata pooled and for individual age strata in the IEP, as well as by sex, by race group (white and non-white), and by ethnicity group (Hispanic or Latino and Not Hispanic or Latino) for all age strata pooled in the IEP. The analysis, both for all age strata pooled and for individual age strata but not for subgroups, is repeated using the mITT population as a measure of robustness of results.

A forest plot is generated to represent seroresponse rate differences between treatment groups at Day 22 for the IEP, both for all age strata pooled and for individual age strata.

8.4.1.2 Day 22 Anti-CHIKV SNA GMT by Treatment Group

Day 22 anti-CHIKV SNA GMTs and associated 95% CIs are compared between PXVX0317 and placebo treatment groups to demonstrate superiority of PXVX0317 vaccine. See Section 6.1 for statistical details.

This endpoint is summarized for all age strata pooled and for individual age strata in the IEP, as well as by sex and by race group (white and non-white) and ethnicity group (Hispanic or Latino and Not Hispanic or Latino) for all age strata pooled in the IEP. The analysis, both for all age strata pooled and for individual age strata but not for subgroups, is repeated using the mITT population as a measure of robustness of results.

A graph of anti-CHIKV SNA GMTs by visit is presented for the IEP population. As well, a reverse cumulative distribution plot of titers by visit is displayed for the IEP population.

8.4.1.3 Day 22 Pairwise Lot Comparison of Anti-CHIKV SNA GMT Ratio in Adults 18 to <46 years (FDA only)

The consistency of the immune response across three consecutively manufactured lots of PXVX0317 vaccine iss confirmed at Day 22 by testing equivalence of anti-CHIKV SNA GMT ratios with associated 95% CIs between all three pairs of PXVX0317 lots (A:B, A:C, B:C) among adults 18 to <46 years of age. See Section 6.1 for statistical details.

This endpoint is summarized in the IEP for the adults 18 to <46 years of age stratum only. The analysis is repeated using the mITT population for the adults 18 to <46 years of age stratum only as a measure of robustness of results.

The seroresponse rate difference (PXVX0317 minus placebo) for each vaccine lot at Day 22 is also assessed as an exploratory endpoint as described in Section 8.4.3.1.

8.4.2 Secondary Immunogenicity Endpoints

8.4.2.1 Key Secondary Immunogenicity Endpoints: Treatment Group Estimates and Difference in Anti-CHIKV SNA Seroresponse Rates at Day 15, Day 183, and Day 8, in that order

The key secondary endpoint of treatment-specific anti-CHIKV SNA seroresponse rates and treatment group difference in seroresponse rates (PXVX0317 minus placebo) and associated 95% CI based on antibody titers measured at Day 15, Day 183, and Day 8 is analyzed as described above for Day 22. For each time point, the null hypothesis of no difference between seroresponse rate percentages in the PXVX0317 vs placebo group is tested using a chi-square test with alpha=0.05. For Day 15 only, the lower bound of the two-sided 95% CI on the difference in seroresponse rates between PXVX0317 and placebo is compared to for assessment of clinical significance.

This endpoint is summarized for all age strata pooled and for individual age strata using the IEP. The analyses are repeated using the mITT population as a measure of robustness of results.

8.4.2.2 Anti-CHIKV SNA GMT at Day 8, Day 15, and Day 183 by Treatment Group

The secondary endpoint of anti-CHIKV SNA GMT and associated 95% CIs for PXVX0317 and placebo based on antibody titers measured at Day 8, Day 15, and Day 183 is analyzed as described above for Day 22.

This endpoint is summarized for all age strata pooled and for individual age strata using the IEP. The analyses are repeated using the mITT population as a measure of robustness of results.

8.4.2.3 GMFI in Anti-CHIKV SNA Titer from Day 1 to Days 8, 15, 22 and 183 by Treatment Group

Geometric mean fold increase over Day 1 (baseline) titer is analyzed as described for GMTs for each post-vaccination time point (Days 8, 15, 22 and 183) by treatment group. See Section 6.1 for statistical details and Section 6.3 for handling of anti-CHIKV SNA titer values below LLOQ.

This endpoint is summarized for all age strata pooled and for individual age strata using the IEP population. Geometric mean fold increase is plotted by visit for the IEP, and a reverse cumulative distribution of fold-rise from baseline by visit is also presented for the IEP.

8.4.2.4 Participants with Anti-CHIKV SNA Titer ≥15 and 4-fold Rise over Baseline at Days 8, 15, 22 and 183 by Treatment Group

Number and percentage of participants with an anti-CHIKV SNA titer ≥ 15 and 4-fold rise over Day 1 (baseline) at Days 8, 15, 22 and 183 are analyzed by treatment group as described for Day 22 seroresponse. See Section 6.1 for statistical details.

This endpoint is summarized for all age strata pooled and for individual age strata using the IEP.

8.4.2.5 If Baseline Seropositive (Anti-CHIKV SNA Titer ≥LLOQ) Rate ≥10%: Treatment Group Difference in Anti-CHIKV SNA Composite Seroresponse Rate at Day 22

If the baseline seropositive (anti-CHIKV SNA titer \geq LLOQ) rate is \geq 10%, difference in anti-CHIKV SNA composite seroresponse rate (PXVX0317 minus placebo) and associated 95% CI at Day 22 are analyzed for the mITT population in the same manner as described above. Composite seroresponse rate is defined in Section 6.3.

This endpoint is summarized for all age strata pooled and for individual age strata using the mITT population.

8.4.2.6 If Baseline Seropositive (Anti-CHIKV SNA Titer ≥LLOQ) Rate ≥10%: Difference in Anti-CHIKV SNA GMT at Day 22 by Treatment Group with Baseline Anti-CHIKV SNA Titer as a Covariate in the ANCOVA Model

If the baseline seropositive (anti-CHIKV SNA titer \geq LLOQ) rate is \geq 10%, difference in anti-CHIKV SNA GMT and associated 95% CIs at Day 22 for PXVX0317 and placebo are analyzed using similar methods to those described above, but with baseline log-transformed anti-CHIKV SNA titer as a covariate in the ANCOVA model for the mITT population.

This endpoint is summarized for all age strata pooled and for individual age strata using the mITT population.

8.4.3 Exploratory Immunogenicity Endpoints

8.4.3.1 Pairwise Lot Differences in Anti-CHIKV SNA Seroresponse Rate at Day 22 in Adults 18 to <46 years

Anti-CHIKV SNA seroresponse rate difference with associated 95% CIs for each pair of PXVX0317 lots (A minus B, A minus C, B minus C) is analyzed in adults 18 to <46 years of age at Day 22 in the same manner as for treatment group seroresponse rate difference. This analysis uses the IEP.

8.5 Pharmacokinetic and Pharmacodynamic Analysis

Not applicable.

9 SAFETY ANALYSIS

All safety data are presented in the form of tabulations and participant listings, based on the safety population.

9.1 Extent of Exposure

The frequencies and percentages of participants receiving IP administration are summarized by treatment group for the randomized population, along with whether or not the dose was administered per protocol (yes/no).

9.2 Adverse Events

The safety of PXVX0317 in healthy adult and adolescent participants 12 to <65 years of age is evaluated using solicited AEs occurring from IP administration on Day 1 through Day 8, unsolicited AEs through Day 29, and AESI and SAEs and MAAEs though Day 183 EOS. AEs are coded to SOC and PT according to the MedDRA dictionary per Section 5.8. They are coded for severity according to Section 5.9 and Appendix II. Only treatment-emergent AEs are summarized (i.e., excluding those after a participant has given informed consent, but before vaccination). See Section 6.3 for definitions.

Solicited AEs, unsolicited AEs, AESI and SAEs and MAAEs are summarized separately by treatment group and maximum severity for the safety population for all age strata combined. Separate participant data listings of solicited and unsolicited AEs sorted by participant identifier and AE start date are generated.

9.2.1 Overall Summary of Solicited and Unsolicited Adverse Events

A high-level summary of solicited and unsolicited AEs combined reviews the frequency counts and percentages of participants by treatment group reporting AEs in each of the following categories:

- Any AE and any AE \geq Grade 3
- Any solicited AE and any solicited AE \geq Grade 3

- Any treatment-related solicited AE and any treatment-related solicited AE \geq Grade 3
- Any unsolicited AE and any unsolicited AE \geq Grade 3
- Any SAE
- Any treatment-related SAE
- Any AE leading to study discontinuation
- Any fatal AE
- Any AESI (see definition in Section 6.3)
- Any MAAE and any treatment-related MAAE

In addition, summaries of combined solicited and unsolicited AEs by SOC, PT and highest reported severity are provided for the following populations:

- Safety population, all age groups
- Safety population by age strata
- Safety population by sex
- Safety population by race group
- Safety population by ethnicity
- Safety population by product lot

9.2.2 Solicited Adverse Events from Day 1 until Day 8

Solicited AEs recorded daily in the e-diary or paper diary until Day 8 include local (i.e., pain, redness, and swelling) and systemic reactions (i.e., fever, chills, fatigue, headache, myalgia, arthralgia, and nausea). In addition, solicited AEs ongoing after seven days post-injection (Day 8) and those that are serious or MAAEs are also recorded as unsolicited AEs. Severity of solicited AEs is assessed by the investigator in the same manner as unsolicited AEs.

Frequencies and percentages of participants experiencing each solicited AE are presented by maximum severity and by treatment group. The following summaries of solicited AEs are produced:

- Solicited AEs by maximum event severity, for each event and for any event
- Solicited AEs of severe (Grade 3) or higher severity, for each event and for any event
- Treatment-related solicited AEs by maximum event severity, for each event and for any event
- Day of first onset of solicited AEs, for each event and any event
- Duration of solicited AEs, for each event and any event
- Solicited AEs by day post-injection for each event and for any event

Occurrence of at least one AE by category (local, systemic) for solicited AEs are also included.

The denominator for solicited AE tables comprises only those participants with at least one diary observation (i.e., any non-missing values but excluding "Not done/unknown"), at least one diary observation for a given symptom, or at least one diary observation for a given day, as applicable. *Note that an elevated in-clinic temperature assessment as part of 30-min post-vaccination vital signs does not count as a solicited AE, as vital signs data are summarized separately.*

9.2.2.1 Electronic Diary Compliance

Participant compliance with e-diary or paper diary solicited adverse event entry are not summarized.

9.2.3 Unsolicited Adverse Events from Day 1 through Day 29

All unsolicited AEs occurring during the specified collection period in the study are recorded, regardless of their assessment of relatedness by the investigator. Unsolicited AEs include also those solicited AEs ongoing after seven days post-injection (Day 8), AESI, and SAEs.

All reported unsolicited AEs are summarized by treatment group according to MedDRA SOC, PT and highest reported severity. When an unsolicited AE occurs more than once for a participant, the maximum severity and closest relationship to treatment is counted. The unsolicited AE analysis includes unsolicited AEs judged by the investigator as at least possibly related to IP.

9.3 Deaths, Other Serious Adverse Events and Other Significant Adverse Events

9.3.1 Deaths from Day 1 to Day 183 End of Study Visit

Deaths are not expected in this study with healthy participants. A tabulation and participant data listing of AEs leading to death are provided.

9.3.2 Serious Adverse Events from Day 1 to Day 183 End of Study Visit

SAEs are tabulated by treatment group according to MedDRA SOC, PT and highest reported severity for all age groups and by age group stratum. A separate tabulation is limited to treatment-related SAEs only. A participant data listing of all SAEs is provided.

9.3.3 Adverse Event of Special Interest from Day 1 to Day 183 End of Study Visit

AESI (see definition in Section 6.3) are tabulated by treatment group according to MedDRA SOC, PT and highest reported severity. In addition, solicited and unsolicited AESI are tabulated together.

9.3.4 Medically Attended Adverse Events from Day 1 to Day 183 End of Study Visit

MAAEs (see definition in Section 6.3) are tabulated by treatment group according to MedDRA SOC, PT and highest reported severity for all age groups and by age group stratum.

9.3.5 Adverse Events Leading to Study Discontinuation from Day 1 to Day 183 End of Study Visit

A participant data listing of all AEs leading to study discontinuation (see definition in Section 6.3) is provided.

9.3.6 Day 1 Adverse Events

A participant data listing of all AEs occurring post-vaccination on Day 1 is generated.

9.4 Clinical Laboratory Tests

Not applicable.

9.4.1 Pregnancy Testing

A participant listing of FSH and pregnancy test results (serum and urine) is created. A listing of pregnancy outcomes, if applicable, is provided.

9.4.2 Viral Serology Testing at Screening

Viral serology testing results are supplied in a participant listing.

9.5 Vital Signs, Physical Findings and Other Variables Related to Safety

9.5.1 Vital Signs

Observed values in vital signs include temperature, blood pressure, respiratory rate, and heart rate at the screening visit and pre- and post-vaccination on Day 1. All vital sign records are displayed in the participant data listings.

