8.7 Safety Analysis

The safety of PXVX0317 in healthy adult and adolescent participants 12 to <65 years of age will be evaluated using solicited AEs occurring from IP administration on Day 1 until Day 8 and unsolicited AEs through Day 29, AESI, MAAEs, and SAEs though Day 183 End of Study Visit, and vital signs. Solicited AEs include local (i.e., pain, redness, and swelling) and systemic reactions (i.e., fever, chills, fatigue, headache, myalgia, arthralgia, and nausea).

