8.7.5 Vital Signs

Vital signs including temperature, blood pressure, respiratory rate, and heart rate at screening and pre- and postvaccination on Day 1 will be summarized by treatment group.

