6.3 Derived Variables

This section provides definitions of the derived variables. In some cases, the definitions are provided in the relevant sections as noted.

AE, causing study discontinuation, is defined as a Yes response to the corresponding question on the AE eCRF.

AE, medically attended (MAAE), is defined as a Yes response to the corresponding question on the AE eCRF.

AE, **related**, is defined as one that is "probably" or "possibly" related to IP per investigator assessment on the eCRF. If the relationship is missing for one or more occurrences of an AE for a given participant, the closest relationship of the remaining occurrences of the AE for that participant is used; if the relationship is missing for the only occurrence of an AE for a given participant, then that event is assumed to be related in order to be conservative.

AE, resulting in death, is defined as a Yes response to the corresponding question on the AE eCRF and/or a fatal outcome.

AE, serious, is defined per the derived eCRF field for AE seriousness, based on the individual criteria that make an AE qualify as serious (results in death, is life-threatening, requires inpatient hospitalization or prolongation of existing hospitalization, results in persistent or significant disability/incapacity, or is a congenital anomaly or birth defect, or any event that may require medical or surgical intervention to prevent one of these outcomes).

AESI is defined in this study as new onset or worsening arthralgia that is medically attended, as noted by an AE having a Yes response to the corresponding AESI question on the AE eCRF.

AE, severity, is graded Grade 1 (mild) to Grade 4 (potentially life-threatening) as described in Section 5.9. If the severity is missing for one or more occurrences of an AE for a given participant, the maximum severity of the remaining occurrences of the AE for that participant is used; if the severity is missing for the only occurrence of an AE for a given participant, then that event is assumed to be severe in order to be conservative.

AEs, solicited, are defined as those collected in the electronic e-diary or paper diary. Solicited AEs include local (i.e., pain, redness, and swelling) and systemic reactions (i.e., fever, chills, fatigue, headache, myalgia, arthralgia, and nausea). *Solicited AEs were to be entered on Day 1 through Day 8; solicited AEs starting on Day 9 or later will be excluded from tabulations, with the exceptions of AESI and SAEs.*

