The denominator for solicited AE tables comprises only those participants with at least one diary observation (i.e., any non-missing values but excluding "Not done/unknown"), at least one diary observation for a given symptom, or at least one diary observation for a given day, as applicable. *Note that an elevated in-clinic temperature assessment as part of 30-min post-vaccination vital signs does not count as a solicited AE, as vital signs data are summarized separately.*

AE, treatment-emergent. AE collection begins at Day 1 (baseline), the day of IP administration. AEs occurring after a participant has given informed consent, but before vaccination, are excluded from summaries. Only treatment-emergent AEs are summarized.

AEs, unsolicited, are defined as those AEs not listed in the e-diary or paper diary but collected in the EDC. Unsolicited AEs were to be collected though Day 29 unless they were SAEs, AESI, or MAAEs; unsolicited AEs starting on Day 30 or later that are not SAEs, AESI, or MAAEs are excluded from tabulations.

Age at screening visit is automatically calculated by EDC based on date of birth versus date of informed consent. Age at baseline (Day 1) is be summarized in all outputs.

Age group strata are defined as ages 12 to <18, 18 to <46, and 46 to <65 as randomized. Note that, if a participant is randomized into a stratum and their age is later corrected such that they should have been placed into a different age stratum, the participant is analyzed according to the corrected age stratum for immunogenicity analyses.

Analysis visits are defined in Section 5.5.

Analysis populations are defined in Section 5.3.

Baseline is defined in Section 5.6. Change from baseline is defined as (value at post-baseline assessment – value at baseline).

Baseline seropositive rate is defined as the percentage of participants with anti-CHIKV human SNA assay titer \geq LLOQ.

Body mass index at screening visit is automatically calculated by EDC as a participant's weight in kg divided by height in m^2 .

Anti-chikungunya virus (anti-CHIKV) human SNA assay NT₈₀ (80% neutralizing titer) is defined as the dilution factor that corresponds to an 80% reduction of luciferase activity compared to virus-only control. Anti-CHIKV SNA titer values below LLOQ are replaced by LLOQ/2 in the immunogenicity analyses including GMT and GMFI. For the 4-fold rise over Day 1 (baseline), values below the LLOQ are replaced with the LLOQ.

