APPENDIX I LIST OF TABLES, FIGURES AND LISTINGS

Note the list of TFLs is a living document and subject to changes during the study.

Table	Title		
Baseline			
14.1.1	Participant Enrollment by Site – Randomized Population		
14.1.2	Analysis Populations – All Participants		
14.1.3	Participant Disposition – Randomized Population		
14.1.4.1	Demography - Randomized Population, All Ages Pooled and by Age Group		
14.1.4.2	Demography – Safety Population, All Ages Pooled and by Age Group		
14.1.4.3	Demography - Modified Intent-to-treat Population, All Ages Pooled and by Age Group		
14.1.4.4	Demography – Immunogenicity Evaluable Population, All Ages Pooled and by Age Group		
14.1.5	Medical History – Randomized Population		
14.1.6	Timing of Blood Sample Collection – Randomized Population		
14.1.7.1	Important Protocol Deviations – Randomized Population		
14.1.7.2	Reasons for Exclusion from Analysis Populations – Randomized Population		
14.1.8.1	Prior and Concomitant Medications by Descending Frequency within ATC Class and Drug Name – Safety Population		
14.1.8.2	Concomitant Vaccines by Descending Frequency within ATC Class and Drug Name – Safety Population		
Immunogenicity			
14.2.1.1.1	Anti-CHIKV SNA Seroresponse Rate by Treatment Group and Visit – Immunogenicity Evaluable Population, All Ages Pooled and by Age Group		
14.2.1.1.2	Anti-CHIKV SNA Seroresponse Rate by Treatment Group and Visit – Immunogenicity Evaluable Population, All Ages Pooled by Sex Subgroups		
14.2.1.1.3	Anti-CHIKV SNA Seroresponse Rate by Treatment Group and Visit – Immunogenicity Evaluable Population, All Ages Pooled by Race Subgroups		
14.2.1.1.4	Anti-CHIKV SNA Seroresponse Rate by Treatment Group and Visit – Immunogenicity Evaluable Population, All Ages Pooled by Ethnicity Subgroups		
14.2.1.2	Anti-CHIKV SNA Seroresponse Rate by Treatment Group and Visit – mITT Population, All Ages Pooled and by Age Group		
14.2.2.1.1	Anti-CHIKV SNA GMT by Treatment Group and Visit – Immunogenicity Evaluable Population, All Ages Pooled and by Age Group		
14.2.2.1.2	Anti-CHIKV SNA GMT by Treatment Group and Visit – Immunogenicity Evaluable Population, All Ages Pooled by Sex Subgroups		
14.2.2.1.3	Anti-CHIKV SNA GMT by Treatment Group and Visit – Immunogenicity Evaluable Population, All Ages Pooled by Race Subgroups		
14.2.2.1.4	Anti-CHIKV SNA GMT by Treatment Group and Visit – Immunogenicity Evaluable Population, All Ages Pooled by Ethnicity Subgroups		

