16.2.2.3	Participants who Received an Excluded Concomitant Medication
16.2.2.4	Important Protocol Deviations
16.2.3	Analysis Populations
16.2.4.1	Demography
16.2.4.2.1	Medical History
16.2.4.2.2	Verbatim to Preferred Term Mapping for Medical History
16.2.4.3	Prior and Concomitant Medications and Vaccines
16.2.4.4	Verbatim to Preferred Name Mapping for Concomitant Medications
16.2.5	Anti-CHIKV SNA Titers
16.2.6	Study Vaccine Administration
16.2.7.1	Solicited Adverse Events
16.2.7.2.1	Unsolicited Adverse Events
16.2.7.2.2	Unsolicited Adverse Events Occurring Postvaccination on Day 1
16.2.7.3	Verbatim to Preferred Term Mapping for Unsolicited Adverse Events
16.2.7.4	Participant Identification of Adverse Events
16.2.8.1	Vital Sign Results
16.2.8.2	Physical Examination Results
16.2.8.3.1	Pregnancy Test Results
16.2.8.3.2	Pregnancy Outcomes
16.2.8.4	Viral Screening Results
16.2.8.5	Hospitalization Details
16.2.8.6	Death Details

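### The SAP plans only a listing for vital signs, so the by-group summary that Protocol 8.7.5 promises, and that the SAP's own exclusion of post-dose in-clinic fever relies on, is not planned

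*SAP*

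**What the plan says.** **Protocol.** Section 8.7 lists what the safety evaluation uses, and the list ends with "SAEs though Day 183 End of Study Visit, and vital signs". Section 8.7.5 then says that temperature, blood pressure, respiratory rate and heart rate "at screening and pre- and postvaccination on Day 1 will be summarized by treatment group". Section 3.3.9 puts the post-dose measurement at 30 minutes to 1 hour after injection.

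**SAP, exclusion rule.** Section 6.3, repeated in 9.2.2, says that an elevated in-clinic temperature from the post-vaccination vital signs "does not count as a solicited AE, as vital signs data are summarized separately".

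**SAP, output.** Section 9.5.1 names the measurements and time points and then gives a single output: "All vital sign records are displayed in the participant data listings". In Appendix I the only matching entry is Listing 16.2.8.1, "Vital Sign Results".

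**The concern.** Two things do not fit together. First, the Protocol promises a summary by treatment group and the SAP specifies a listing. No SAP text states or justifies a departure. Second, the SAP gives a reason for keeping post-dose in-clinic fever out of the solicited AE tables, and that reason points to an output that the SAP does not define. This is an inconsistency within the SAP as well as between the two documents.

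At stake is a descriptive safety output under the coprimary safety objective. The vital signs are the scheduled, staff-measured readings taken shortly after injection. A programmer who follows SAP 9.5.1 and Appendix I would give the reader of the study report only individual records. That reader could not see from any planned table how the readings were distributed in each group, or how many participants had a raised temperature soon after dosing.

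**Working it through.** No figure in the plan is at issue, so the check sets the texts side by side.

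1. **Does a listing satisfy Protocol 8.7.5?** No. Protocol 8.7.4, immediately before it, says that physical examination data are to be listed, while 8.7.5 says that vital signs are to be summarized by treatment group. The Protocol uses different words for the two outputs in adjacent sections.

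2. **Does any SAP section define the summary?** Section 9.5.1 gives listings only. Section 9.2 restates the Protocol's list of safety evaluations but leaves vital signs out. Section 6.2 sets reporting precision for vital-sign means and SDs, and section 6.1 describes summary statistics for continuous endpoints. Neither section specifies a vital-signs table.

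3. **Does Appendix I supply it?** Count of entries titled for vital signs: tables 0, figures 0, listings 1 (16.2.8.1). None of the safety entries from 14.3.1 to 14.3.5.12 is a vital-signs table.

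4. **Where does a raised post-dose in-clinic temperature go?**
   - *Solicited AE tables:* excluded by SAP 6.3 and 9.2.2. Solicited AEs "are defined as those collected in the electronic e-diary or paper diary".
   - *Unsolicited AE tables:* no default route. SAP 6.3 defines unsolicited AEs as those not listed in the diary, and fever is a diary item.
   - *Vital-signs table:* none planned.
   - *Listing 16.2.8.1:* yes.

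   So the reading itself enters no planned table.

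5. **Can the same event still be tabulated?** Yes, by several routes.
   - The participant takes a daily oral temperature (Protocol 3.3.10). If a diary reading reaches 38.0 °C, the fever is a solicited AE.
   - Solicited events that are serious, medically attended or ongoing after Day 8 are also recorded as unsolicited AEs (SAP 9.2.2).
   - Any unfavorable sign can be an AE (Protocol 7.1.1), and AEs revealed by observation go on the AE eCRF (Protocol 7.2). Heart-rate and blood-pressure changes are not diary items, so when reported as AEs they fall in the unsolicited tables.

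6. **Volume of data.** If all 3150 planned participants are dosed and measured, Day 1 gives 3150 × 2 = 6300 sets of vital signs, and screening adds 3150. This shows only how much is left to a listing. It does not measure an effect.

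**The case against.** The strongest reply is that the SAP meant to include the table and left out its title. SAP section 9 opens with "All safety data are presented in the form of tabulations and participant listings", section 6.2 gives precision rules that a listing would not need, and the exclusion rule itself asserts that vital signs are summarized. Appendix I also carries the note "Note the list of TFLs is a living document and subject to changes during the study", and Protocol 8.7.5 remains in force. That is a fair account of the likely intent. It does not remove the gap, because the body text of 9.5.1, and not only the changeable list, specifies listings alone. These passages support adding the table.

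The reply is right on three stronger readings that a reader might draw and that the documents do not support:

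- *That post-dose fevers, or acute vital-sign changes generally, are tabulated nowhere.* The diary and AE routes above remain open. What has no planned table is the in-clinic readings as measured, including those not judged to be AEs.
- *That vital signs are the only objective acute safety data.* Diary temperature is taken with a supplied thermometer, and redness and swelling are measured with a supplied ruler, from Day 1. They are graded on numeric cut-offs (SAP 5.9 and Appendix II).
- *That a planned between-group comparison is lost.* Protocol 8.7.5 promises a descriptive summary. Vital signs are not among the safety endpoints in Protocol 8.3.1, and Protocol 8.6.2.5.2 reports all safety endpoints for information only.

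**Conclusion.** The point holds as an inconsistency that should be corrected. The SAP as written does not plan the vital-signs summary that Protocol 8.7.5 commits to, and its rule on post-dose in-clinic fever rests on a summary that it does not define.

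The size is modest: one missing descriptive table. Fever within an hour of injection is likely to be rare, so the effect on the solicited fever rate is expected to be small. That is a judgment, since the documents give no rate. No endpoint, hypothesis test or success criterion changes.

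The conclusion rests on the SAP text and on the output titles in Appendix I. The table shells that accompany the SAP were not available. If they already contain a vital-signs table, what remains is to bring 9.5.1 and Appendix I into line with them.

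**What to change.** Add one table to SAP 9.5.1 and Appendix I: vital signs in the safety population by treatment group, for all ages pooled and by age group (as Protocol 8.7.8 asks of summaries), at screening, before dosing and after dosing on Day 1. Include the number and percentage with a post-dose temperature at or above 38.0 °C. The standard statistics in SAP 6.1 would show the maximum temperature but not how many participants were febrile, and that count is what supports the exclusion in 6.3 and 9.2.2. Restore vital signs to the list of safety evaluations in SAP 9.2.

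Change from before to after dosing, and counts of the other abnormalities graded in Protocol Appendix I, would be useful. Protocol 8.7.5 does not require them.

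If the sponsor prefers to keep a listing only, the SAP should state and justify the departure from Protocol 8.7.5, and the reason given in 6.3 and 9.2.2 should be reworded.

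The cost is one extra table from data already collected.
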